### **Study Design**

# Research questions.

- I. Does learning about adult ADHD lead to a higher rate of self-diagnosis and worse self-reported symptoms?
- II. Does learning about the role expectations play on one's mental health at the same time as getting the ADHD information reduce this effect?

# Primary hypotheses.

- I. Healthy participants who learn about symptoms of undiagnosed ADHD in adults will report higher rates of those symptoms and a higher rate of self-diagnosis with ADHD than healthy participants learning neutral information (control group).
- II. Participants who learn about nocebo effects at the same time as learning about ADHD will have fewer symptoms and lower rate of self-diagnosis after watching the videos compared to the ADHD group.

# Dependent variables (primary outcomes).

- a. Inattentive ADHD symptoms, as measured by the subscale of Adult ADHD Self-Report Scale (ASRS)
- b. Hyperactive ADHD symptoms, as measured by the subscale of Adult ADHD Self-Report Scale (ASRS)
- c. ADHD self-diagnosis, as measured by an item on a 5-point Likert scale

**Study conditions**. We will test participants in groups. We will use block randomization (1:1:1) and assign each participant group to one of the three conditions:

- d. ADHD group
- e. ADHD + Nocebo education group
- f. Control group

#### **Statistical Analysis Plan**

**Primary analyses.** We will use a mixed-effects model to predict each outcome variable outlined in the measures given the condition (ADHD, ADHD + nocebo, control) at one-week follow-up, with the covariate of baseline symptoms, as well as a random intercept for each participant (and group in which they were tested). We will use Tukey's test to compare all pairs of means for each outcome.

We will run directional tests and use Type I error rate of 0.05 for all the tests without correcting for family-wise error given the small number of tests.

**Secondary analyses.** If the sample is adequately powered, will also run subgroup analyses on the dependent variables based on participants' gender.

**Data exclusions.** We will exclude participant data points before computing statistical analyses if one of the following conditions is met.

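### Does a participant random intercept in a model of one-week scores, with apparently one row per participant, require a change to the primary analysis?

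*Combined protocol and SAP*

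**What the plan says.** The Primary analyses paragraph predicts each outcome "given the condition (ADHD, ADHD + nocebo, control) at one-week follow-up". The same sentence continues: "with the covariate of baseline symptoms, as well as a random intercept for each participant (and group in which they were tested". Baseline enters as a covariate, so it is not an outcome row, and there are two random intercepts, one for the participant and one for the testing group. Pairwise comparison follows, using Tukey's test "to compare all pairs of means for each outcome". No time term, condition-by-time term or item-level analysis is mentioned.

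Under Dependent variables, two outcomes are ASRS subscales and the third is a single item: "ADHD self-diagnosis, as measured by an item on a 5-point Likert scale". Study conditions gives the unit of assignment; the investigators "assign each participant group to one of the three conditions".

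Hypothesis II gives no exact time. It says that participants in the nocebo-education arm "will have fewer symptoms and lower rate of self-diagnosis after watching the videos compared to the ADHD group". The exclusion rules mention one follow-up survey, with a limit of 8 days after the study.

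**The concern.** The sentence that defines the primary model seems to pull two ways. A single named time, with baseline on the right-hand side, gives one row per participant for each outcome. A participant intercept has something to estimate only when participants contribute several rows. Either the term is surplus or some rows are not described.

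If the term is surplus, the literal model cannot be identified and the analyst must depart from it. If further post-video rows were intended, a model with a participant intercept but no condition-by-time term estimates an average over times. A claim about one week could then rest on an effect present only straight after the videos. Choosing between the two models after seeing the data would add flexibility to tests that the plan leaves uncorrected.

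**Working it through.** The documents give no sample size, ICC or effect size, so there is no stated figure to reproduce. The checks are whether the model can be identified, and what would follow from the alternative reading.

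**1. Rows implied by the text.** There is one outcome time (Primary analyses), a separate model for each outcome, baseline as a covariate, and one self-diagnosis item. That gives one row per participant per model.

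**2. Algebra for one row each.** For participant i in testing group j, y = Xβ + g_j + p_i + e_i, with variances σ²_g, σ²_p and σ²_e. The covariance matrix is V = σ²_g ZZ′ + (σ²_p + σ²_e) I. Only the sum σ²_p + σ²_e appears. The estimate (X′V⁻¹X)⁻¹X′V⁻¹y and its covariance (X′V⁻¹X)⁻¹ depend on V alone, so the split between participant and residual cannot affect them.

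**3. Numerical check.** Assumed: 30 testing groups of 5 (150 participants), σ²_g = 0.09 and σ²_p + σ²_e = 1.0. Participant shares of 0, 0.25, 0.5, 0.75 and 0.99 all gave:

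- REML log-likelihood −80.054634
- condition estimates 0.5282 and 0.24311
- standard errors 0.24134 and 0.24111

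With two rows per participant in a second simulated data set, the log-likelihood did depend on the share: −166.42 at 0, −123.58 at the true value 0.64 and −126.51 at 0.75. The term is therefore surplus with one row and useful with two.

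**4. If an immediate post-video score also existed.** Assumed: 30, 60 or 90 per arm in groups of 6, ICC 0.02–0.10, correlation 0.5–0.8 between the two scores, and uncorrected one-sided 5% contrasts. Pooling without a time interaction estimates (immediate effect + one-week effect)/2.

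| Effects in SD (immediate, one week) | Pooled estimate | Consequence |
|---|---|---|
| 0.5, 0 | (0.5 + 0)/2 = 0.25 | pooled model rejects in 19–56% of trials; one-week model in 4.8–5.2% |
| 0.5, 0.25 | 0.75/2 = 0.375; 0.375/0.25 = 1.5, so 50% too large | the two models disagree on significance in 13–38% |
| 0.25, 0.5 | 0.75/2 = 0.375; 0.375/0.5 = 0.75, so 25% too small | at 60 per arm, power is 51–70% pooled against 70–82% one-week |
| 0, 0, model chosen afterwards | – | type I error 5.9–7.2% instead of 5% |

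A longitudinal model that reports the one-week condition contrast avoids this. With 60 per arm, correlation 0.7, ICC 0.05 and effects (0.5, 0), rejection was 5.2% from one-week rows, 37.3% pooled and 5.1% from the one-week contrast. In six REML fits that contrast matched the one-week model within 0.001.

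**5. The intercept that does matter.** If the testing-group intercept were dropped, the one-sided error would be 1 − Φ(z₀.₉₅/√DE), with DE = 1 + (m − 1)·ICC. For assumed group size m and ICC:

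- m = 3, ICC 0.01: DE = 1.02, error 0.052
- m = 5, ICC 0.05: DE = 1.2, error 0.067
- m = 10, ICC 0.10: DE = 1.9, error 0.116

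The plan already lists this term.

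**The case for a change.** The best case for a change is that the model cannot be fitted exactly as written and that correcting the sentence costs almost nothing. If the named time settles the rows, the participant term contradicts it. If the term is deliberate, rows are missing from the description, and the loose timing in hypothesis II leaves room for an immediate rating. An analyst faced with a singular fit might also remove the wrong random effect.

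The literal fit problem stands. The consequences drawn from it are weaker.

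- **Extra time point.** One week later is also after the videos, so hypothesis II does not conflict with the named time. No section describes an immediate rating. Even if one was taken, pooling it would set aside the stated time point, whereas the one-week contrast from a longitudinal model would respect both the time point and the participant intercept.
- **Item-level rows.** ASRS items would also give the term a purpose, but the plan names subscales. With complete items in a linear model, the contrast would be the same one on a per-item scale.
- **Ordinal or binary self-diagnosis.** Here a participant variance informed by one row each would move the odds ratio. However, the plan compares means, and hypothesis I uses the word rates for symptoms too, so the word does not signal another model. In simulated ordinal data (180 participants, participant SD fixed at 0 to 3) the z statistic moved by at most 0.32, so decisions would change only near the threshold.
- **Removing the wrong term.** Conditions are assigned to testing groups, and the plan names the group intercept for that structure. Removing it would be a departure from the plan.

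**Conclusion.** The inconsistency is genuine but is best read as surplus wording. Following the named time point, an analyst fits the one-week score on condition, baseline and a testing-group intercept. The participant term drops out with no change in any condition estimate or standard error. The loss is at most a failed or singular fit that is resolved at once.

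This rests on one row per participant and a linear model, as the text indicates. The 19–56% rejection rate and the 13–38% disagreement apply only if an undocumented immediate score were pooled with the one-week score, and they also depend on assumed sample sizes, ICCs, correlations and effects. Stating which rows enter would make the paragraph tidier, but it would not alter the analysis a careful analyst would run. No change is needed.

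### Taken literally, the plan adjusts the self-diagnosis outcome for baseline symptoms and not for its own baseline; if the item is asked at baseline, leaving it out costs precision

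*Combined protocol and SAP*

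**What the plan says.** The Primary analyses paragraph of the Statistical Analysis Plan describes a single model form for all outcomes: "We will use a mixed-effects model to predict each outcome variable outlined in the measures given the condition". The analysis is "at one-week follow-up", "with the covariate of baseline symptoms", with random intercepts for participant and testing group. No other covariate is named.

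The section Dependent variables (primary outcomes) lists two ASRS symptom subscales, inattentive and hyperactive, and then a third outcome: "ADHD self-diagnosis, as measured by an item on a 5-point Likert scale". The research questions and the primary hypotheses also name symptoms and self-diagnosis as two different things.

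Under Study conditions, allocation is 1:1:1 and by testing group: the plan will "assign each participant group to one of the three conditions". On error control, the plan says "We will run directional tests and use Type I error rate of 0.05 for all the tests", with no family-wise correction.

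The documents do not say whether the self-diagnosis item is asked before the videos. They also do not say whether the symptom covariate is a total score or the matching subscale.

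**The concern.** For the two symptom outcomes, the natural reading of the covariate is the outcome's own baseline, and only the choice of score is left open. For self-diagnosis, the same words point to a related but different variable. What a person believed about having ADHD before the videos would then enter the model only through its correlation with symptoms.

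Two things are at stake, both conditional on a baseline value existing. The first is precision: variation between people that prior belief explains, and symptoms do not, stays in the residual. The second is chance imbalance: if one arm happens to start with more people who already think they have ADHD, adjusting for symptoms removes only part of that difference. Research question I is partly about self-diagnosis, so a reader of the results may ask whether the arms started level on it.

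**Working it through.** **Reading the text.** The model sentence covers every outcome and names one covariate. The plan lists self-diagnosis apart from symptoms in the outcomes, and keeps the two apart in the research questions and hypotheses. Followed to the letter, the self-diagnosis model contains baseline symptoms and not baseline self-diagnosis.

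**No figure to reproduce.** The documents give no sample size, power, SD, correlation or intraclass correlation. Every number below is an assumption or follows from one.

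**Inputs (all assumed).**
- rs = correlation of baseline symptoms with follow-up self-diagnosis: 0.3 to 0.5
- rd = correlation of baseline with follow-up self-diagnosis: 0.2 to 0.7
- c = correlation of the two baseline measures: 0.4
- starting power 80%, one-sided 0.05 (the sidedness and level are the plan's)

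**Formulas.** With symptoms only, residual variance is 1 − rs². With both covariates it is 1 − (rs² + rd² − 2·rs·rd·c)/(1 − c²). The proportional reduction equals the squared partial correlation:

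r_p² = (rd − rs·c)² / [(1 − rs²)(1 − c²)]

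Power after the change = Φ[(1.645 + 0.842)/√(1 − r_p²) − 1.645].

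**Example.** rs = 0.3, rd = 0.7: (0.7 − 0.12)² / (0.91 × 0.84) = 0.3364/0.7644 = 0.440. At the other end, rs = 0.5, rd = 0.2: (0.2 − 0.20)² / (0.75 × 0.84) = 0.

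| rs | rd | Residual variance, symptoms only | Residual variance, both | Reduction | Power from 80% |
|---|---|---|---|---|---|
| 0.3 | 0.2 | 0.91 | 0.90 | 0.8% | 80.3% |
| 0.3 | 0.3 | 0.91 | 0.87 | 4.2% | 81.5% |
| 0.3 | 0.5 | 0.91 | 0.74 | 18.9% | 86.8% |
| 0.3 | 0.7 | 0.91 | 0.51 | 44.0% | 95.3% |
| 0.5 | 0.2 | 0.75 | 0.75 | 0% | 80.0% |
| 0.5 | 0.3 | 0.75 | 0.74 | 1.6% | 80.6% |
| 0.5 | 0.5 | 0.75 | 0.64 | 14.3% | 85.1% |
| 0.5 | 0.7 | 0.75 | 0.45 | 39.7% | 94.0% |

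The table ignores clustering.

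**Chance imbalance.** The SD of the difference between two arms in baseline self-diagnosis, in SD units, is √(2·DE/n), with DE = 1 + (m − 1)·ICC. With n = 50 per arm and no clustering it is √(2/50) = 0.20. With groups of m = 10 and ICC 0.05, DE = 1.45 and it is √(2.9/50) = 0.24. For n = 100 per arm the two values are 0.14 and 0.17. With ICC = 0, assigning whole groups adds nothing.

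If the arms differ by 0.2 SD in prior self-diagnosis in a way that symptoms do not reflect, the symptom-adjusted contrast moves by 0.2 × (rd − rs·c)/(1 − c²). At rs = 0.3, rd = 0.5 this is 0.2 × 0.38/0.84 = 0.09 SD. It is 0 at rs = 0.5, rd = 0.2, and 0.2 × 0.58/0.84 = 0.14 SD at rs = 0.3, rd = 0.7.

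**The case against.** The strongest reply is that there may be nothing to adjust for. The plan mentions only baseline symptoms, and leaving the item out of the baseline survey could be deliberate: asking people before the videos whether they think they have ADHD could reveal what the study is about, and suspicion about its purpose appears among the data exclusions. The documents do not give this as a reason, but it is plausible. This objection stands, so the loss cannot be called avoidable without knowing what is collected.

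A second reply is that the covariate phrase may be shorthand for each outcome's own baseline. The participant random intercept cannot be separated from residual error with one follow-up value per person, so repeated measures including baseline may have been meant. Neither is stated. If that was the intent, clearer wording would record it.

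Third, the gain may be trivial. Hypothesis I concerns healthy people, and a floor effect on a single 5-point item could make its baseline a weak predictor. This stands, and it is why the range starts at zero.

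A reader might also infer that omitting prior self-diagnosis biases the result, or that assigning whole groups makes imbalance a serious threat. The documents do not support either. Randomisation protects the comparison on average, and chance imbalance is part of ordinary sampling error. Group assignment enlarges it only if prior belief clusters within testing groups, about which the documents are silent. The testing-group random intercept is there to carry such variation into the standard error, and baseline symptoms absorb part of any imbalance. Adjusting for symptoms alone is a valid prespecified analysis.

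**Conclusion.** The point holds in a conditional form. On the literal text, one of three primary outcomes is adjusted for a different construct. If the self-diagnosis item is asked at baseline, leaving it out gives up precision and adjusts only partly for chance imbalance in prior belief. Average bias and type I error are not at issue.

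The size cannot be derived from the documents. With the correlations assumed above and clustering ignored, the reduction in residual variance is about 0-4% at an own-baseline correlation of 0.2-0.3, 14-19% at 0.5 and 40-44% at 0.7. Quoting only the upper part of that range, as a gain of 14-44%, would be tempting but would rest on favourable assumptions alone.

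It is still worth correcting before analysis. The covariate set for a primary outcome should not be left to the analyst, particularly with one-sided tests at 0.05 and no family-wise correction.

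**What to change.** In the Primary analyses paragraph, replace "with the covariate of baseline symptoms" with wording such as: *each model adjusts for the baseline value of its own outcome: the matching ASRS subscale for each symptom outcome and, where the item is collected at baseline, the baseline self-diagnosis item in addition to baseline symptoms for self-diagnosis.* State in the same place whether the item is in the baseline survey.

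If it is not collected, keep baseline symptoms, entered as both ASRS subscales, and say plainly that prior self-diagnosis is not adjusted for. This fallback settles the specification but does not recover the lost adjustment. The item should not be added to the baseline survey solely for this purpose, given the risk of cueing participants to the aim.

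The cost is a sentence or two of SAP text and, where the item exists, one extra covariate in one model. No new data are needed.

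### Does the gender subgroup analysis need a stated method and power criterion before it can be run?

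*Combined protocol and SAP*

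**What the plan says.** The Statistical Analysis Plan, under Secondary analyses, says: "If the sample is adequately powered, will also run subgroup analyses on the dependent variables based on" gender. That is the whole provision. It does not define the power condition (which effect, what level, judged when), the gender categories, or whether gender enters as an interaction or as a stratifying variable.

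The primary model, one paragraph earlier, predicts each outcome from condition, "with the covariate of baseline symptoms, as well as a random intercept for each participant (and group in which they were tested"). It contains no gender term. Two general rules might carry over to the gender analysis: "We will run directional tests" and "We will use Tukey's test to compare all pairs of means for each outcome".

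The research questions and primary hypotheses concern condition only. Neither mentions gender.

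**The concern.** A subgroup analysis by gender, in a plan whose model has no gender term, is easily read as the same comparisons repeated in each gender. Such tests ask whether condition has an effect in women and whether it has one in men. They do not ask whether the two effects differ. When the true effects are equal, chance alone will often put one p-value below 0.05 and the other above it, and a reader may take that pattern as evidence that gender modifies the effect.

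The power condition adds to the unease. With no criterion, the decision to run or report the analysis could be taken after the data are seen. At stake would be a spurious statement about gender in a secondary section of the report.

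**Working it through.** The documents state no sample size, power, effect size or gender split, so there is no figure of the plan's own to reproduce. What follows is illustrative.

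**Inputs from the documents.** Error rate 0.05 per test, directional; three outcomes; three pairwise contrasts per outcome; whole testing groups randomised ("We will use block randomization (1:1:1) and assign each participant group to one of the three conditions").

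**Assumed.** Two gender categories of equal size; one contrast; the same true effect in both genders; large-sample normal tests.

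**1. Chance of significance in exactly one gender.** With independent subgroups and power p in each, this is 2p(1 − p).
- p = 0.80: 2 × 0.80 × 0.20 = 0.32.
- p = 0.90: 2 × 0.90 × 0.10 = 0.18.

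These depend only on p, so applying Tukey's critical value within gender would not alter them.

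**2. Shared testing-group error.** If groups are mixed by gender, part of the error is common to both estimates. Let ρ be the share of the whole-sample contrast variance that is common. A gender-specific estimate then has relative variance v = ρ + (1 − ρ)/0.5, and the two estimates have correlation r = ρ/v.
- ρ = 0.1: v = 1.9, r = 0.053.
- ρ = 0.5: v = 1.5, r = 0.333.

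Discordance is 2p − 2P(both significant), taken from the bivariate normal. At p = 0.80 it is 0.312 and 0.261 for the two values of ρ. At p = 0.90 it is 0.177 and 0.154.

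**3. If only the whole sample has 80% power.** At one-sided 0.05 the whole-sample effect is 1.645 + 0.842 = 2.487 standard errors. In each half it is 2.487 × √0.5 = 1.758, so power per gender is Φ(1.758 − 1.645) = 0.545. Discordance is 2 × 0.545 × 0.455 = 0.496 with independent subgroups. It falls to 0.476 at ρ = 0.1 and 0.360 at ρ = 0.5.

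**4. What an interaction test would deliver.** It flags identical effects 5% of the time. Suppose the gender difference is as large as the main effect, each gender has 80% power, and no error is shared. The noncentrality is then 2.487/√2 = 1.758, and two-sided power is 0.42. If the 80% power refers to Tukey's critical value of 2.344, the noncentrality is (2.344 + 0.842)/√2 = 2.253 and power is about 0.61. If only the whole sample has 80% power, without Tukey, the noncentrality is 2.487/2 = 1.243 and power is about 0.24.

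**5. Do these results bear on anything the plan states?** The plan does not specify separate tests, does not exclude an interaction, and has no rule by which significance in one gender would be reported as a gender difference. Steps 1 to 3 measure the cost of one way of running the analysis combined with one misreading of its result. They do not show an error in a stated rule.

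**The case for a change.** The strongest case for a change is that it would be nearly free. One sentence naming a condition-by-gender term, and one extra model per outcome, would block a foreseeable misreading and close an undefined trigger. No new data would be needed. The low power of an interaction test is no defence of separate tests, since they hide the imprecision instead of showing it. The general directional rule also fits poorly, because no direction is hypothesised for a gender difference.

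Much of this stands. The method and the criterion are absent, and separate tests do not answer the question of effect modification. An analyst wishing to claim a gender difference would need the interaction, estimated two-sided in the primary model with the testing-group intercept kept, and with categories and any power trigger settled before the data are seen.

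Two parts do not stand. The complaint that the analysis is not labelled exploratory carries little weight, because it is already placed under Secondary analyses and both hypotheses are labelled primary. Nor do the percentages turn an omission into an error: they rest on assumed inputs and move materially with shared group error, Tukey's critical value and the gender split.

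**Conclusion.** No change to the plan is called for. The gap is real but small: an optional secondary analysis is named without its method. Harm requires three things in turn: the power condition is judged to be met, the analysis is run as separate tests, and the results are then read as a comparison between genders. The plan commits to neither the second nor the third.

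If that chain did occur, the chance of a contrast significant in one gender only, with identical true effects, would be 32% or 18% at 80% or 90% power per gender with equal, independent subgroups. It would be 26% or 15% if half the contrast variance were shared. If only the whole sample had 80% power, it would be about 50% with none shared and 36% with half shared. All of this depends on the assumed power, equal split, two categories and degree of sharing.

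The within-gender tests would themselves be valid for the effect in each gender, and the primary comparisons would be untouched. An analyst who wants to speak about gender differences has a standard route in the interaction term, and nothing in the plan bars it.
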